### **5.5 Anticipated Total Enrollment**

Up to a total of 357 subjects shall be enrolled into the WAVE Study across both cohorts. Up to 40% of the total enrollment for each cohort may be enrolled outside of the US. No site may enroll more than 20% of the total enrollment per cohort.

## **6.0 STUDY PROCEDURES**

### **6.1 Visit Schedule**

Study participation will last for a total of 24 months ( $\pm 75$  days). Traditional visit windows are being expanded to allow for potential impacts due to COVID-19. Subjects will be enrolled in the acute phase of the study. Study clinic visits and data collection during the acute phase will be completed at index procedure, 30 days ( $\pm 10$  days), 6 months (180 days  $\pm 30$  days) and 12 months (360 days  $\pm 45$  days); telephone visits will be completed at 3 months (90 days  $\pm 15$  days), 9 months (270 days  $\pm 30$  days) and 18 months (540 days  $\pm 45$  days). A final post-market surveillance follow-up visit will be performed at 24 months (720 days  $\pm 75$  days).

A summary schedule of the required study tests and evaluations is in **Table 9**:

## 6.2 Baseline

[figure not shown]
The following examinations and tests will be performed. For those study procedures that are not considered standard of care (performed only for study participation), they will be performed after the subject signs the informed consent form in order to meet **all** inclusion and **no** exclusion criteria. These examinations and tests will be used both to screen eligible subjects and provide baseline information for those subjects that meet study eligibility criteria.

*All tests must be completed within the 30 days prior to undergoing the index / study procedure, except for the pregnancy test, which must be completed within 14 days of the procedure (if applicable).*

- Demographic information and medical history including, but not limited to, risk factors and hemodialysis and dialysis access history:
  - Type, location and date of all previous venous outflow circuit intervention(s)
  - Prior dialysis access type(s) and location(s)
    - Location of current dialysis access, including date AVF or AVG was first used for dialysis
- Targeted physical examination, including but not limited to:
  - Height and weight
  - Vascular access circuit / fistula assessment including, but not limited to:
    - Presence / absence of steal syndrome
    - Presence / absence of thrill
    - Presence / absence of bruit
    - Presence / absence of infection
- Laboratory Assessments:
  - Urine or serum pregnancy test if female of child-bearing potential (within **14** days of procedure). NOTE: Please review your institutions standard for women of childbearing potential.

### 6.3 Medications

Effective anticoagulation therapy should be maintained throughout the procedure with heparin (per hospital or institutional standards) or a clinically acceptable alternative of the treating physician's choice. There is no current requirement for dual antiplatelet therapy for this therapeutic area and treatment modalities. Treatment with antiplatelet and/or anticoagulation post-procedure is per investigator discretion for the best interest and safety of the subject.

### **6.4.3. Randomization**

Randomization will be used to reduce potential bias during data collection and evaluation of clinical endpoints in the AVF Peripheral cohort. Randomization schedules will be generated using block randomization that will control the balance of treatment groups within each site and across the study. It is not possible for treating physicians to be blinded to the treatment group. Subjects who receive a Merit WRAPSODY Stent Graft must receive a device information card to provide to health care givers in the event they undergo an MRI, so subjects cannot be blinded.

AVF Peripheral subjects will be randomized 1:1 to receive either the Merit WRAPSODY Stent Graft (SG) or PTA. AVG Anastomosis subjects will not be randomized. Once baseline angiography confirms eligibility, including confirmation of reference vessel diameter (RVD), lesion length, full expansion of the predilatation balloon, the patient is eligible to be randomized or enrolled in the AVF Anastomosis cohort.

Subjects randomized to the PTA arm (control) will undergo standard percutaneous balloon angioplasty. Subjects randomized to receive treatment with the Merit WRAPSODY Stent Graft after predilatation will undergo stent graft placement as outlined in Section 6.4.4. Only the target lesion will be treated with the WRAPSODY stent graft.

Note: Subjects in the AVG Anastomosis cohort will all receive treatment with the Merit WRAPSODY Stent Graft as this cohort is non-randomized.

#### **6.4.3.1. Randomization Errors**

Randomization was built in the EDC system with multiple safeguards to prevent randomization, including but not limited to, verification of treatment cohort (e.g., AVF, AVG anastomosis) prior to proceeding with randomization. In the event that a randomization error occurs, the subject will continue to be considered enrolled.

### **6.4.4. Implant Procedure**

Refer to the Instructions for Use (IFU) for a description of the implant procedure. Additional data captured during the procedure include, but may not be limited to:

- Baseline angiographic criteria assessment

- Location of stent graft placement using angiographic radiopaque ruler during index procedure
- Assessment of post-stent graft implantation lumen patency via angiogram at the conclusion of the index procedure (percent angiographic stenosis and angiographic patency of  $\leq 30\%$  residual stenosis at target site)
- Evaluation of total procedure time
- Determination of blood loss and replacement
- Identification of technical difficulties
- Adverse event observation, evaluation, and treatment
- At the conclusion of the index procedure, a final angiographic cine showing the entire vascular access circuit is required (per Angiographic Core Lab Protocol) to assess for procedural- and/or device-related complications.

### 6.5 Day 30 Follow-Up – Clinic Visit

The following evaluations will be scheduled for **Day 30** ( $\pm 10$  days) post procedure:

- Targeted physical examination, including but not limited to:
  - Physical assessment of fistula / access circuit including, but not limited to:
    - Presence / absence of steal syndrome

- Presence / absence of thrill
- Presence / absence of bruit
- Presence / absence of infection
- Dialysis status including, but not limited to:
  - Access blood flow
  - Arterial and venous pressures
  - Ipsilateral extremity edema
  - Clot aspiration during dialysis
  - Prolonged bleeding from puncture site
  - Dialysis flow rates
- Medication assessment (antiplatelets, anticoagulation medications)
- Adverse event assessment, including interventions on the venous outflow circuit

Note: In situations where investigator for the site does not oversee the subject's hemodialysis, measures shall be taken to obtain the necessary information for the applicable visits by their hemodialysis provider.

### **6.6 Month 3 Follow-Up – Telephone Visit**

The following evaluations will be scheduled for **Month 3** (90 days  $\pm$  15 days) post procedure:

- Medication assessment (antiplatelets, anticoagulation medications)
- Adverse assessment, including interventions on the venous outflow circuit

### **6.7 Month 6 Follow-Up – Clinic Visit**

The following evaluations will be scheduled for **Month 6** (180 days  $\pm$  30 days) post procedure:

- Targeted physical examination, including but not limited to:
  - Physical assessment of fistula / access circuit including, but not limited to:
    - Presence / absence of steal syndrome
    - Presence / absence of thrill
    - Presence / absence of bruit
    - Presence / absence of infection
  - Dialysis status including, but not limited to:
    - Access blood flow
    - Arterial and venous pressures
    - Ipsilateral extremity edema
    - Clot aspiration during dialysis
    - Prolonged bleeding from puncture site
    - Dialysis flow rates
- Medication assessment (antiplatelets, anticoagulation medications)
- Adverse assessment, including interventions on the venous outflow circuit

Note: In situations where investigator for the site does not oversee the subject's hemodialysis, measures shall be taken to obtain the necessary information for the applicable visits by their hemodialysis provider.

### **6.8 Month 9 Follow-Up – Telephone Visit**

The following evaluations will be scheduled for **Month 9** (270 days  $\pm$  30 days) post procedure:

- Medication assessment (antiplatelets, anticoagulation medications)
- Adverse assessment, including interventions on the venous outflow circuit

### 6.9 Month 12 Follow-Up – Clinic Visit

The following evaluations will be scheduled for **Month 12** (360 days  $\pm$  45 days) post procedure:

- Targeted physical examination, including but not limited to:
  - Physical assessment of fistula / access circuit including but not limited to:
    - Presence / absence of steal syndrome
    - Presence / absence of thrill
    - Presence / absence of bruit
    - Presence / absence of infection
  - Dialysis status including, but not limited to:
    - Access blood flow
    - Arterial and venous pressures
    - Ipsilateral extremity edema
    - Clot aspiration during dialysis
    - Prolonged bleeding from puncture site
    - Dialysis flow rates
- Medication assessment (antiplatelets, anticoagulation medications)
- Adverse assessment, including interventions on the venous outflow circuit

Note: In situations where investigator for the site does not oversee the subject's hemodialysis, measures shall be taken to obtain the necessary information for the applicable visits by their hemodialysis provider.

### 6.10 Month 18 Follow-Up – Telephone Visit

The following evaluations will be scheduled for **Month 18** (540 days  $\pm$  45 days) post procedure:

- Medication assessment (antiplatelets, anticoagulation medications)
- Adverse assessment, including interventions on the venous outflow circuit

### 6.11 Month 24 Follow-Up – Clinic Visit (Post-Market Surveillance Phase of the Study)

The following evaluations will be scheduled for **Month 24** (720 days  $\pm$  75 days) post procedure:

- Targeted physical examination, including but not limited to:
  - Physical assessment of fistula / access circuit including, but not limited to:
    - Presence / absence of steal syndrome
    - Presence / absence of thrill
    - Presence / absence of bruit
    - Presence / absence of infection
  - Dialysis status including, but not limited to:
    - Access blood flow
    - Arterial and venous pressures
    - Ipsilateral extremity edema
    - Clot aspiration during dialysis
    - Prolonged bleeding from puncture site
    - Dialysis flow rates
- Medication assessment (antiplatelets, anticoagulation medications)
- Adverse assessment, including interventions on the venous outflow circuit

Note: In situations where investigator for the site does not oversee the subject's hemodialysis, measures shall be taken to obtain the necessary information for the applicable visits by their hemodialysis provider.

### **6.13 Vascular Access Interventions**

In the event that a subject requires an intervention to either the target lesion or elsewhere within the access circuit, the investigational site should provide sufficient documentation regarding the clinical and physiological signs and symptoms requiring the need for interventions, including but not limited to, status of thrill, bruit, infection, decreased dialysis pump flows, limitations to effective dialysis treatment, increased venous pressures, etc. Reinterventions to the target lesion and elsewhere within the access circuit shall follow the KDOQI Guidelines (2019). Such reinterventions shall only be performed on those subjects that have a clinically relevant lesion requiring intervention for resolution of clinical symptomatology. Reinterventions on lesions that are not clinically symptomatic should be avoided until such a time that the lesion is clinically symptomatic.

Angiography should only be performed if reintervention is deemed necessary from clinical and physiological symptoms. All procedural angiograms should be recorded at the same angles and views as taken during the index procedure, where possible. All images should be taken per core laboratory manual.

## **7.0 ADVERSE EVENTS**

All adverse events will be recorded and documented throughout the 12-month visit. Following the 12-month visit, only serious adverse events (SAE) and unanticipated adverse device effects (UADE) will be recorded and documented through the 24-month follow-up visit.

The Investigator at each participating center is ultimately responsible for reporting adverse events to the Sponsor. The adverse event electronic case report form (eCRF) provides a venue for the Investigator to record any adverse event data. The Investigator should follow all unresolved serious adverse events until the events are resolved, the subject is lost to follow-up, the subject has withdrawn consent, the subject completes the study, or the adverse event is otherwise explained.

The Sponsor shall review all adverse events for their relationship to the study device(s) and/or procedures and comparative anticipated safety event rates. The Sponsor will conduct evaluations of any unanticipated device-related event per standard operating procedures.

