### 4.2 Secondary Outcome Measures

1. Proportion of subjects with Target Lesion Primary Patency at months 12 and 24.
  2. Proportion of subjects with Assisted Target Lesion Primary Patency (aTLPP) at months 6, 12 and 24 defined as time to loss of Assisted Primary Patency of the target lesion, which is the time from post-procedure until uncorrectable target lesion occlusion.
  3. Proportion of subjects with Access Circuit Primary Patency (ACPP) at months 6, 12 and 24 defined as time to loss of Primary Patency of the access circuit, which is the time from post-procedure until any venous outflow circuit re-intervention, or access thrombosis or abandonment.
  4. Proportion of subjects with Post-Procedure Secondary Patency at months 6, 12 and 24 defined as the interval post-procedure until access circuit abandonment.
  5. Rates of procedure- and device-related adverse events involving the access circuit at index procedure, 30 days, and months 6, 12 and 24.
- 

[figure not shown]
[figure not shown]

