### 7.1 Adverse Event

For the purposes of this study, an adverse event (AE) is any untoward medical occurrence, unintended disease or injury, or untoward clinical signs in subjects, whether or not related to the investigational device or procedure. In addition, the definition of AE applies to any event with an onset during enrollment / index procedure or to any underlying diseases, present at baseline, that exacerbate in severity post study procedure. Therefore, an underlying disease that was present at the time of enrollment is not reported as an AE, but any increase in the severity of the underlying disease is to be reported as an AE. This definition includes events occurring during the follow-up period.

All reported AEs through 12 months must be recorded in the electronic database. Following the 12-month visit, only SAEs and UADEs will be recorded in the electronic database. A description of the event, including the start date, resolution date (or final outcome assessment date), action taken, and the outcome should be provided, along with the Investigator's assessment of the severity, seriousness, the relationship between the AE, the study device and the study procedure.

The following definitions for rating severity of adverse events will be used:

- Mild: Awareness of signs or symptoms, but easily tolerated; are of minor irritant type; causing no loss of time from normal activities; symptoms would generally not require medication or a medical evaluation; signs or symptoms are transient (e.g., headache treated with acetaminophen, common cold, etc. would be considered mild).
- Moderate: Interferes with the subject's usual activity and/or requires symptomatic treatment.
- Severe: Symptom(s) causing severe discomfort and significant impact of the subject's usual activity and requires treatment.

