### **7.3 Adverse Event Reporting**

#### **7.3.1. General Reporting Requirements**

All serious and potentially device- and/or procedure-related adverse events must be recorded on the Adverse Event electronic CRF by the Investigator (or designee). The report should include: severity, duration, action taken, treatment outcome and relationship of the adverse experience to the study device, procedure, concomitant medications, pre-existing condition, (i.e., unrelated, related or relationship unknown).

In the case of serious adverse events, device-related adverse events, target lesion and access circuit interventions, and potential device malfunctions and failures, medical record documentation (e.g., procedure notes, operative notes, discharge summary, relevant progress notes, imaging, or lab studies) must be provided to the Sponsor or its designee as requested for safety adjudication by the Clinical Events Committee (CEC).

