#### **7.3.2. Reporting Requirements for Serious Adverse Events**

All serious adverse events must be reported by the Investigator (or designee) to the Sponsor within 24 hours of knowledge of the event or by the end of the next working day. This may be done via phone, fax, email or electronic data capture for the clinical database.

The Investigator (or designee) shall send a written report including a narrative description of the serious adverse event to the Sponsor or their designee within five (5) working days of the initial report. This can also be in the form of the AE eCRF.

Any serious adverse events and all deaths regardless of cause may need to be reported to the IRB / EC per local IRB / EC requirements. It is the responsibility of the Investigator to inform their IRB / EC of these serious adverse events as required by their IRB / EC procedures and in conformance with FDA and local regulatory requirements. In addition, the investigator shall provide documentation of the IRB / EC report to Merit Medical or its designee.

All adverse events (AE) will be monitored from the time of enrollment through the 12-month assessment. SAEs and UADEs as well as vascular access circuit events will be monitored from the time of enrollment through the follow-up period for this trial (24 months). A description of the event, including the start date, resolution (or date of final outcome assessment) date, action taken, and the outcome should be provided, along with the Investigator's assessment of the relationship between the AE and SAE and the study treatment.

All AEs should be followed until the event is resolved or judged to be chronically stable. The clinical site should plan to provide relevant AE follow-up information to the Sponsor upon request.

The Sponsor or its designee will report all applicable serious adverse events as vigilance reports per MEDDEV 2.12.1, Rev 8 (2013) "Guidelines on a Medical Devices Vigilance System" and as clinical study reportable events per MEDDEV 2.7/3 "Clinical Investigations: Serious Adverse Event Reporting," MDCG 2020-10/1 "Guidance on safety reporting in clinical investigations" and EU MDR 2017/745 "The European Union Medical Device Regulation of 2017". The Sponsor will determine whether all of the local Investigators need to be informed immediately of an SAE or UADE, or whether this can be postponed until the next regularly scheduled study update.

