### 9.5 Other Safety Data

All adverse events (AEs) collected will be coded. Events will be summarized cumulatively through the following time points: 30 days, 6 months, 12 months (all AEs) and 24 months (SAEs only). Frequency count of AEs and unique number of patients who had the AEs, for each coded term, will be presented. Also, the frequency and percentage of patients who had a Serious AE (SAE), or a related AE (by relationship to both implant procedure and device) will be tabulated separately by a coded term.

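### Secondary endpoint 5 needs related access-circuit events of any seriousness to month 24, but the protocol contradicts itself on whether non-serious ones are recorded after month 12

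*Combined protocol and SAP*

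**What the plan says.** Section 4.2, item 5 (also in the Protocol Summary) sets the endpoint: "Rates of procedure- and device-related adverse events involving the access circuit at index procedure, 30 days, and months 6, 12 and 24". It carries no seriousness limit. Section 7.1 treats a serious device effect as a device-related event that also meets a seriousness criterion, so non-serious related events fall within the endpoint.

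Three places narrow what is kept after the first year:

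- Section 7.0 opens with "All adverse events will be recorded and documented throughout the 12-month visit". After that visit, "only serious adverse events (SAE) and unanticipated adverse device effects (UADE) will be recorded and documented through the 24-month follow-up visit".
- Section 7.1 applies the same limit to data entry: "Following the 12-month visit, only SAEs and UADEs will be recorded in the electronic database".
- Section 9.5 plans cumulative summaries, the last two being "12 months (all AEs) and 24 months (SAEs only".

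Two places point to wider capture:

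- Section 7.3.2: "SAEs and UADEs as well as vascular access circuit events will be monitored from the time of enrollment through the follow-up period for this trial", with 24 months given as the end.
- Section 7.3.1: "All serious and potentially device- and/or procedure-related adverse events must be recorded on the Adverse Event electronic CRF". No time limit is attached.

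The month-18 and month-24 contacts (sections 6.10 and 6.11) include an adverse event assessment that covers outflow-circuit interventions. Section 12.10 gives the Clinical Events Committee all pre-specified endpoints and all site-reported conduit interventions through end of study. Under section 9.10, secondary endpoints outside the named testing hierarchy are descriptive, and endpoint 5 is not in that hierarchy.

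**The concern.** A site that works from sections 7.0 and 7.1 will not enter a non-serious device- or procedure-related access-circuit event with onset after month 12. A site that works from section 7.3.2 may well enter it. The month-24 rate could then rest on different capture rules at different sites, and on a different event definition from the rates at 30 days and months 6 and 12.

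The device is a permanent implant. Section 3.2 places the 24-month visit in the post-market phase and says the study is to meet post-market requirements for CE marking. Section 8.1.1 lists stent graft compression, kinking, migration and strut fracture among the risks. These belong to the implant, so in the randomized AVF cohort a loss of late non-serious events need not be equal between the arms. Endpoint 5 is where such events would be reported as a rate.

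**Working it through.** The plan states no rate for this endpoint, so there is no figure to reproduce. The check sets the rules side by side for one kind of event: non-serious, device- or procedure-related, involving the access circuit, with onset between months 12 and 24.

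| Place | What it governs | Is this event covered? |
|---|---|---|
| 4.2, item 5 | Endpoint definition | Yes |
| 7.0 | Recording | No |
| 7.1 | Database entry | No |
| 7.3.1 | Adverse event eCRF | Yes, no time limit stated |
| 7.3.2 | Monitoring to 24 months | Apparently yes |
| 9.5 | 24-month summary | No |
| 12.10 | Committee review | Only if reported |

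Two details decide how far the conflict reaches.

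1. *The UADE exception.* Section 7.1 describes a UADE in terms of serious effects or serious problems. Keeping UADEs after month 12 therefore recovers essentially none of the non-serious events.
2. *The reach of section 7.3.2.* It speaks of monitoring, whereas section 7.1 expressly limits what enters the database. Section 13 defines the access circuit but not an access circuit event, so the added category has no stated boundary.

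**Illustration of size.** All inputs here are assumptions; none comes from the documents. Let p be the cumulative proportion with a related access-circuit event at month 12, h the risk of a first such event in months 12 to 24 among those still event-free, and s the share of those year-2 subjects whose events are non-serious.

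- True 24-month proportion = p + (1 − p)h
- Recorded proportion under 7.0 and 7.1 = p + (1 − p)h(1 − s)
- Shortfall = (1 − p)hs

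With p = 10%, h = 5% and s = 50%:

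- True: 0.10 + 0.90 × 0.05 = 14.5%
- Recorded: 0.10 + 0.90 × 0.05 × 0.50 = 12.25%
- Shortfall: 2.25 percentage points

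Over p from 5 to 20%, h from 2 to 10% and s from 25 to 75%:

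- Smallest shortfall: 0.80 × 0.02 × 0.25 = 0.4 points, on a true 21.6% (about 2% of it)
- Largest shortfall: 0.95 × 0.10 × 0.75 = 7.1 points, on a true 14.5% (about 49% of it)

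If section 7.3.2 governs and the events are entered and analysed, nothing is dropped and the shortfall is about zero.

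**Comparability.** A month-24 table of serious events only is a different quantity from an all-event table at month 12. In the example above, if half the affected subjects in both years had only non-serious events, the serious-only figure at month 24 would be 0.5 × 14.5% = 7.25%, below the all-event 10% at month 12. A cumulative series of one quantity cannot fall in this way.

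**The case against.** The strongest reply is that the protocol does provide for these events. Section 7.3.2 extends to 24 months the very category that endpoint 5 concerns. The same paragraph uses the word monitored for ordinary adverse events up to month 12 and goes on to ask for start date, resolution date, action taken and outcome, so it can fairly be read as a recording rule. Section 7.3.1 requires related events on the eCRF without a time limit, and the late contacts assess adverse events. This stands to the extent that loss of data is not certain. It does not settle the matter, because sections 7.0 and 7.1 both use an express restriction, and nothing says which section prevails. Committee review does not close the gap either: an event managed without intervention and never entered cannot be adjudicated.

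Section 9.5 is a summary rule for other safety data. It does not stop any recording, and it is not shown to be the analysis of endpoint 5. Section 9.4 is not visible in the public text and may hold that analysis. Section 9.5 also labels the change of scope openly, so a reader of those tables would be told of it, and one should not assume that they would be taken to show events levelling off in year 2.

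A reader might also infer that about half of all non-serious related events would be lost, since half the follow-up lies after month 12. That needs even accrual, which the documents do not support. The endpoint includes procedure-related events, counted from the index procedure, and section 5.4 withdraws subjects at transplant, explant or access abandonment, which shortens year-2 exposure. A fraction of the non-serious count is in any case not a fraction of the endpoint rate.

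**Conclusion.** The inconsistency is real and should be corrected. Sections 7.0 and 7.1 conflict with secondary endpoint 5 and with sections 7.3.1 and 7.3.2, and section 9.5 plans a narrower 24-month summary than the endpoint describes. The understatement is conditional: it arises if 7.0 and 7.1 are applied as written and is about zero if 7.3.2 is applied through to analysis. A flat statement that the month-24 rate will be understated goes further than the documents allow.

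The size cannot be determined from the documents; the range in the working rests wholly on assumed inputs. The consequence is limited. The endpoint is descriptive, and the 24-month data go into a post-submission report (section 9.10). The 30-day safety endpoint, the 6-month patency endpoint, the sample size and the error control are untouched.

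**What to change.** Reconcile the passages in one of two ways.

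- **(a) Keep the endpoint.** Amend 7.0, 7.1 and 9.5 so that device- and procedure-related access-circuit events of any seriousness are recorded in the eCRF and summarized through month 24. Define the access circuit event category used in 7.3.2. Require retrospective entry for subjects already past month 12; otherwise the amendment would itself mix two capture rules.
- **(b) Narrow the endpoint.** Restrict the month-24 component of endpoint 5 to related SAEs and UADEs, and report the same serious-only rates at index, 30 days and months 6 and 12. Without those earlier rates the series is still not comparable.

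Option (a) preserves the late safety information. Option (b) remains available even where year-2 follow-up has already passed.

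The cost is a short amendment, with FDA and IRB/EC approval where section 12.3 requires it, an eCRF completion note and a small amount of extra data entry. The month-18 and month-24 contacts already include an adverse event assessment, so no new visit is needed. Retrospective entry under (a) is the main added work, since enrollment began in March 2021 and some subjects may be past month 12 when the change takes effect.
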